## 6. Study Design

This study is a multi-center, single arm study in insulin-requiring subjects with type 1 diabetes who are 14 years of age and older. The run-in period will be approximately up to 35 days long, followed by a study period that will be approximately up to 33 days in duration.

The study is anticipated to last no longer than 13 months from investigational center initiation to completion of all data entry and monitoring procedures. The study will target approximately 5 months to complete subject enrollment. Subjects can expect to participate for approximately 2-3 months including the run-in and study periods.

A total of up to 75 subjects (aged 14-75) will be enrolled at a minimum 2 investigational centers and up to 6 investigational centers (hospitals) in China to have at least 50 subjects who complete the study.

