#### **Study Period :**

---

*Medtronic Confidential*

The study period begins at Visit 4 in which subjects will begin using Auto Mode. The subject will have follow up visits after Auto Mode has been turned on to adjust insulin pump settings and then continue wearing the study devices until the end of the study period.

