## 9. Study Procedures

### 9.1. Study Timeline

#### Visit Schedule:

#### **Run-in Period Visits: To be completed approximately up to 35 days**

[figure not shown]
- Visit 1: Screening (Office):
  - Consent
  - Collect demographic and baseline characteristics:
    - Age
    - Gender
    - Race
    - Ethnicity
    - Height and Weight
  - Obtain prior Medical History
  - Collect concomitant medications
  - Labs (pregnancy test [if applicable], HbA1c, TSH, Hct, GA and eGFR)
  - Screening Requirements
- Visit 2: Run-in Period Start - Visit 2 (Office): 2 - 7 days after Visit 1
  - ***Eligibility has been confirmed including labs***
  - **All eligible subjects:**
    - Start study pump; provide pump training
    - Collect questionnaire(s)
    - Collect information about food consumed in last 24 hours (food log)
  - Subjects who are using pump **with** CGM at Screening:
    - Visits 2 and 3 may be combined
    - Start CGM, provide CGM training
    - Start CGM run-in (2 weeks)
    - Install Mobile App to Smartphone (if applicable)
    - System is set Manual Mode (Sensor Augmented Pump only):  

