**SmartGuard™ features should not be activated**

#### Study Period Visits:

*Medtronic Confidential*

- Visit 4 (Office): 14 days after Visit 3 (+7 days)
  - Turn on Auto Mode
- Visit 5 (Office/ Telephone): 1 days after Visit 4 Office or telephone visit
  - Adjust settings as needed
- Visit 6 (Office/ Telephone): 2 days after Visit 4 Office or telephone visit
  - Adjust settings as needed
- Visit 7 (Office/ Telephone): 3 days after Visit 4 Office or telephone visit
  - Adjust settings as needed
- Visit 8 (Office/ Telephone): 4 days after Visit 4 Office or telephone visit
  - Adjust settings as needed
- Visit 9 (Office/ Telephone): 5 days after Visit 4 Office or telephone visit
  - Adjust Settings as needed
  - Provide training as needed
- Visit 10 (Office) – 14 days after Visit 4 (+3 days)
- Visit 11 (Office) – 20 days after Visit 4 ( $\pm 3$  days)
- Visit 12 (Office) – 30 days after Visit 4 ( $\pm 3$  days)
  - Remove Mobile App from Smartphone (if applicable)
  - Collect questionnaire(s)
  - Collect lab test for GA
  - End of Study

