### 9.11.2. Stopping Rules for Entire Study

During the study period, the following steps will be taken for:

- Unanticipated Adverse Device Effects (UADE)
  - Device related Diabetic Ketoacidosis (DKA)
  - Device related Severe hypoglycemia
1. Site will notify the sponsor within approximately 24 hours of receiving knowledge of the event.
  2. CEC is to review and adjudicate the event.
  3. CEC will provide recommendation to the sponsor on the following:
    - a) If enrollment and the study may continue
    - b) If enrollment should be stopped, while already enrolled subjects are allowed to continue in study
    - c) If the entire study must be stopped, including subjects who have already received study devices.

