## 10. Risks and Benefits

### 10.1. Potential Risks

---

*Medtronic Confidential*

Risks with Infusion Sets	Prevention and Mitigation

Risks with infusion sets may include:
 

• Localized infection

• Skin irritation/redness

• Bruising

• Discomfort/pain

• Bleeding

• Irritation

• Rash

• Hyperglycemia secondary to infusion set occlusion or infusion site failure including DKA

• Hyperglycemia secondary to site falling off including DKA

• Anxiety associated with insertion

	
Prevention and mitigation include:
 

• Follow the provided user guides for insertions and care of infusion sets.

• If an infusion site becomes irritated or inflamed, the infusion set should be removed and another placed in a new location.

• In case of hyperglycemia secondary to infusion set occlusion, remove current infusion set and replace with new infusion set and give correction insulin if needed with syringe.

• Follow the provided user guides for insulin pump management.

• Training prior to study on device use and diabetes management principles and told to call with problems.

Risks with Insulin Administration and Pumps	Prevention and Mitigation

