
Risks with the use of an insulin infusion pump may include the risk of malfunction of the components of the system (pump, software, infusion set and reservoir) as well as the risk of use error during use of the system. Device deficiencies or use errors can result in administration of too much or too little insulin which can lead to the following clinical consequences:
 

• Hypoglycemia

• Hyperglycemia

• Diabetic ketoacidosis

• Severe hypoglycemia with or without associated seizure, coma or death

• Kinked cannula leading to hyperglycemia

• Infusion set disconnection from pump leading to hyperglycemia

• Subject removes the reservoir from the pump but forgets to disconnect the infusion set from the body which results in hypoglycemia or severe hypoglycemia

• Dislodged cannula leading to hyperglycemia

	
Prevention and mitigation include:
 

• Follow the provided user guides & instructions for insulin pump management which includes information on infusion set change.

• Training prior to study on device use and diabetes management principles and told to call with problems.

• Check SMBG 4-6 times a day and also before driving (as applicable). Instructed to have glucose on hand for hypoglycemia

• Change infusion set if suspected catheter occlusion or administer insulin with syringe for persistent hyperglycemia especially if ketones develop.

• A pump error may lead to under delivery or over-delivery of insulin

• Battery failure – no insulin delivered

• Insulin deterioration leading to hyperglycemia

• Incomplete priming; fails to prime tubing and/or cannula, leading to hyperglycemia

• Remove a reservoir, without suspending and reconnecting after a while resulting in a Hypoglycemia

• Patient not filling pump reservoir when needed leading to hyperglycemia

• Magnetic Resonance Imaging resulting in pump transmitter malfunction

• Inaccurate insulin delivery due to sudden altitude changes.

• Hypoglycemia or hyperglycemia from manual bolus

• Hypoglycemia or Hyperglycemia from the use of the Auto Mode feature where sensor glucose values may be used to calculate insulin bolus amounts

• Hypoglycemia or hyperglycemia from computer hacking

	

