## 11.3. Reporting of Adverse Events

The investigator or designee will record ALL AEs while the subject is enrolled in the clinical study. Each AE needs to be assessed for its device or procedure relatedness. A device related AE is associated with the use of the study device (e.g. infection of sensor site or infusion set occlusion resulting in DKA). A procedure related AE is associated with testing related to the study procedures specified in the CIP (e.g. IV insertion pain).

Examples of device or procedure related AEs include:

- **Device** related (ADE): insertion site infection
- Serious adverse **device effect**: cellulitis at device insertion site requiring hospitalization
- **Procedure** related AE: bruising at IV insertion site

Subjects participating in the study have diabetes and are expected to experience hypoglycemia and or hyperglycemia. These normal events are not expected to be reported to sponsor on an AE eCRF as this is not considered an untoward event, but rather an expected occurrence. Any glycemic excursion that meets the protocol definition of Severe Hypoglycemia, Severe Hyperglycemia or DKA is considered an untoward event and a worsening from the subject's baseline and would be reported to sponsor on an AE eCRF.

Baseline medical conditions should only be reported to sponsor on an AE eCRF if there is a worsening from the subject's baseline. For example, a subject previously diagnosed with Asthma is hospitalized for severe asthma attack would be a reportable event.

Adverse events will be documented in the subject source file and reported to sponsor on an eCRF. The investigational center is responsible for documentation of AEs including obtaining source documents related to the event, such as emergency medical technician/paramedic reports, hospital records (admission summary; lab results, test results, discharge summary) or device uploads to support the event. Source documents will be reviewed to determine if additional AEs have occurred and require reporting.

Narratives gathered from completed questionnaires will not provide the basis of an AE report however could lead to discussions that result in the identification of a reportable AE.

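### The whole-study stopping rule starts at Visit 4, so a device-related event on the investigational pump during run-in does not oblige a CEC recommendation

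*Protocol*

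**What the plan says.** Protocol Section 9.11.2, and the matching row of the Synopsis, open with "During the study period, the following steps will be taken for" and name three triggers: UADE, device-related DKA and device-related severe hypoglycemia. The site notifies the sponsor within about 24 hours, the CEC adjudicates, and the CEC recommends one of three courses: carry on, close enrollment only, or stop the study for everyone.

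Section 6 treats run-in and study period as consecutive and separate: "The run-in period will be approximately up to 35 days long, followed by a study period". It also fixes the boundary: "The study period begins at Visit 4 in which subjects will begin using Auto Mode". SAP Section 5 repeats this.

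The pump is listed as investigational in Table 1. Section 9.1 puts its start at Visit 2 for every eligible subject: "Start study pump; provide pump training". During run-in it works as a sensor-augmented pump with the SmartGuard features off (Section 6).

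Section 10.1 lists harms that do not need Auto Mode. For infusion sets it names "Hyperglycemia secondary to infusion set occlusion or infusion site failure including DKA". For pumps it says "Device deficiencies or use errors can result in administration of too much or too little insulin which can lead to the following clinical consequences", and the list that follows includes DKA and severe hypoglycemia. Section 11.3 gives "infusion set occlusion resulting in DKA" as an example of a device-related adverse event.

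**The concern.** Take the protocol's own example, DKA after an infusion set occlusion. After Visit 4, that event obliges the CEC to adjudicate and to advise on the whole study. The same event on the same pump in the week before Visit 4 does not, as the rule is written.

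The CEC is made up of external physicians and is the only committee that Section 12 describes. What is at stake is therefore an independent, cross-site opinion on whether enrollment or the study should go on after an early device-related event. The time limit also fits poorly with the rule's own remedies. Closing enrollment acts at consent (Section 8.2). Stopping the whole study reaches subjects who already hold devices, and pumps are handed out at Visit 2 (Table 3). Run-in subjects can be stopped under the rule, yet their own events do not trigger it.

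**Working it through.** **1. Is the term used strictly?** The primary endpoint is a change from run-in to study period (Section 14.6.1), and the ITT set is defined by entry to the study period (Section 14.5). Neither makes sense if the term includes run-in. Section 9.10 uses broader wording when it means the whole of a subject's participation, and Section 9.11.1, directly above the rule, has no period limit.

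**2. What else covers a run-in event?**

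| Provision | Applies in run-in? | Obliges a CEC recommendation? |
|---|---|---|
| Subject withdrawal for DKA or severe hypoglycemia (9.11.1) | Yes | No |
| Sponsor notification, desired within 24 hours (11.4) | Yes | No |
| SAE reports to authorities and EC; written comments on continuing or stopping for other AEs and device deficiencies (Table 4) | Yes | No |
| Sponsor report to authorities within 5 working days (Table 5) | Yes | No |
| CEC review of listed events (12.1) | Permitted | No; permissive, and refers back to 9.11.2 |
| Sponsor or regulator suspension or termination (16.11) | Yes | No |
| Investigator's assessment at the center (16.11.1) | Yes | No |

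**3. Time on the pump outside the rule.** Inputs are the visit windows in Section 9.1: Visit 1 to 2, 2–7 days; Visit 2 to 3, 0–7 days; Visit 3 to 4, 14–21 days; Visit 4 to 12, 30 ± 3 days.

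- Check on the plan's own figures: maximum run-in 7 + 7 + 21 = 35 days, and maximum study period 30 + 3 = 33 days. Both match Section 6.
- Pump wear before Visit 4: 0 + 14 = 14 days to 7 + 21 = 28 days.
- Pump wear inside the rule: 27 to 33 days.
- Share of a completer's pump time outside the rule: lowest 14/(14 + 33) = 14/47 = 30%; highest 28/(28 + 27) = 28/55 = 51%.
- Start of the trial: even with the shortest windows, the first 14 days of pump wear by anyone fall outside the rule. Taking the planned 5-month enrollment as 150 days, that equals 14/150 = 9.3% of it.

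**4. How many events might this involve?** Section 4.1.2 reports no severe hypoglycemia or ketoacidosis in 12,389 patient-days in the US trial. With zero events, the rule-of-three 95% upper bound on the daily rate is 3/12,389. Multiplied by run-in pump days:

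| Wearers | 14 days each | 28 days each |
|---|---|---|
| 50 (target completers) | 700 days: 0.17 | 1,400 days: 0.34 |
| 75 (enrollment ceiling) | 1,050 days: 0.25 | 2,100 days: 0.51 |

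The exact Poisson limit (2.996 in place of 3) changes nothing at two decimals except 0.51, which becomes 0.508 rather than 0.509. Seventy-five is a ceiling because enrollment is counted at consent, so some enrolled subjects may never start the pump. The bound counts events from any cause, so the device-related number is smaller. The documents give no UADE rate, so UADE is not included.

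**The case against.** **The phrase may be loose drafting.** Section 15.1 says technical support is provided during the study period, while the Synopsis has device deficiencies reported to Technical Support from enrollment onward. The rule's enrollment and device-holder options are also study-wide. The sponsor may well have meant to cover run-in. If so, the text should say so, because Sections 6, 14.5 and 14.6.1 use the term strictly and nothing redefines it for Section 9.11.2.

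**The limit may be deliberate.** In run-in, Auto Mode is off, and subjects have had more than 6 months of pump therapy. Attaching an extra review step to the closed-loop phase is coherent. But the protocol does not give this reason, the pump itself is investigational, and Section 10.1 lists DKA and severe hypoglycemia as pump risks without Auto Mode.

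**The remaining gap is small.** This stands. The CEC output is advice to the sponsor, and the other provisions apply from consent or pump start.

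A reader might infer more than the documents support:

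- *That run-in events go unreported, or that the study could not be stopped for them.* Sections 9.11.1, 11.4 and 16.11 and Tables 4 and 5 rule this out.
- *That the CEC may not look at run-in events.* Section 12.1 has no period limit; it only fails to require the review.
- *That the unprotected start is 16 days.* The earliest Visit 4 is 2 + 0 + 14 = 16 days after first consent, but no study pump is worn before Visit 2, so 14 days is the relevant figure.
- *That the change can cost at most half a CEC review.* The 0.51 is an upper bound on an expected count. At a Poisson mean of 0.51, the chance of at least one event is 1 − exp(−0.51), about 40%, and UADE would come on top.

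**Conclusion.** The point holds in a narrow form. Between Visit 2 and Visit 4, no provision obliges the CEC to adjudicate a UADE, device-related DKA or device-related severe hypoglycemia, or to advise on the whole study. This covers 14 to 28 days of investigational pump wear per subject, about 30% to 51% of a completer's pump time. Pump, infusion set and sensor events are affected; Auto Mode events are not.

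The reading rests on taking the study period as Section 6 defines it. The event bound of 0.17 to 0.51 rests on a borrowed rate: Section 4.1.2 does not say whether the 12,389 patient-days include run-in, and that trial's study phase was 3 months of Auto Mode. The bound scales directly with the rate, so a true upper limit twice as high would give about 0.34 to 1.02.

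This is a low-weight safety correction. It does not affect the sample size, the primary test or any analysis set.

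**What to change.** In Section 9.11.2 and the Synopsis, replace the opening time limit with: *From first use of the study pump (Visit 2) to end of study*. In Section 12.1, state that the CEC will review the events named in Section 9.11.2 from that same start.

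The cost is one wording amendment with EC approval and possibly an occasional extra CEC review. No visits, procedures or data collection are added, because these events are already recorded from consent.

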## 10. Risks and Benefits

### 10.1. Potential Risks

---

*Medtronic Confidential*

Risks with Infusion Sets	Prevention and Mitigation

Risks with infusion sets may include:
 

• Localized infection

• Skin irritation/redness

• Bruising

• Discomfort/pain

• Bleeding

• Irritation

• Rash

• Hyperglycemia secondary to infusion set occlusion or infusion site failure including DKA

• Hyperglycemia secondary to site falling off including DKA

• Anxiety associated with insertion

	
Prevention and mitigation include:
 

• Follow the provided user guides for insertions and care of infusion sets.

• If an infusion site becomes irritated or inflamed, the infusion set should be removed and another placed in a new location.

• In case of hyperglycemia secondary to infusion set occlusion, remove current infusion set and replace with new infusion set and give correction insulin if needed with syringe.

• Follow the provided user guides for insulin pump management.

• Training prior to study on device use and diabetes management principles and told to call with problems.

Risks with Insulin Administration and Pumps	Prevention and Mitigation

Risks with the use of an insulin infusion pump may include the risk of malfunction of the components of the system (pump, software, infusion set and reservoir) as well as the risk of use error during use of the system. Device deficiencies or use errors can result in administration of too much or too little insulin which can lead to the following clinical consequences:
 

• Hypoglycemia

• Hyperglycemia

• Diabetic ketoacidosis

• Severe hypoglycemia with or without associated seizure, coma or death

• Kinked cannula leading to hyperglycemia

• Infusion set disconnection from pump leading to hyperglycemia

• Subject removes the reservoir from the pump but forgets to disconnect the infusion set from the body which results in hypoglycemia or severe hypoglycemia

• Dislodged cannula leading to hyperglycemia

	
Prevention and mitigation include:
 

• Follow the provided user guides & instructions for insulin pump management which includes information on infusion set change.

• Training prior to study on device use and diabetes management principles and told to call with problems.

• Check SMBG 4-6 times a day and also before driving (as applicable). Instructed to have glucose on hand for hypoglycemia

• Change infusion set if suspected catheter occlusion or administer insulin with syringe for persistent hyperglycemia especially if ketones develop.

• A pump error may lead to under delivery or over-delivery of insulin

• Battery failure – no insulin delivered

• Insulin deterioration leading to hyperglycemia

• Incomplete priming; fails to prime tubing and/or cannula, leading to hyperglycemia

• Remove a reservoir, without suspending and reconnecting after a while resulting in a Hypoglycemia

• Patient not filling pump reservoir when needed leading to hyperglycemia

• Magnetic Resonance Imaging resulting in pump transmitter malfunction

• Inaccurate insulin delivery due to sudden altitude changes.

• Hypoglycemia or hyperglycemia from manual bolus

• Hypoglycemia or Hyperglycemia from the use of the Auto Mode feature where sensor glucose values may be used to calculate insulin bolus amounts

• Hypoglycemia or hyperglycemia from computer hacking

	
Risks with hyperglycemia may include: 

• Diabetic ketoacidosis

• Symptomatic ketosis

• Cardiovascular event

• Dehydration

• Potassium and sodium imbalance

• Shock

• Altered mental status

• Coma

• Acidosis

	Prevention and mitigation include: 

• Follow the provided user guides for insulin pump management.

• Training prior to study on device use and diabetes management principles.

• Check SMBG 4-6 times a day.

• Alternative method of managing glucose levels should be available (insulin and syringe for example)

Risks with hypoglycemia may include: 

• Seizure

• Coma

• Altered mental status

• Loss of consciousness

• Cardiovascular event

• Death

• Risk of rebound hyperglycemia with ketosis

	Prevention and mitigation include: 

• Follow the provided user guides for insulin pump management.

• Training prior to study on device use and diabetes management principles.

• Check SMBG 4-6 times a day.

• Instructed to have glucose on hand for hypoglycemia

Risk with Sensors	Prevention and Mitigation
Risks with Sensors may include: 

• Skin irritation or reaction to adhesives

• Bruising

• Discomfort

• Redness

• Bleeding

• Excessive bleeding due to anticoagulants

• Pain

• Rash

• Infection

• Irritation from tapes used with glucose-sensing products

• Raised bump

• Appearance of a small "freckle-like" dot where needle was inserted

• Allergic reaction

• Syncopal episode secondary to needle insertion

• Soreness or tenderness

• Swelling at insertion site

• Sensor fracture, breakage or damage

• Minimal blood splatter associated with sensor needle removal

• Residual redness associated with adhesive and/ or tapes

• Scarring

• Scab

• Blister

• Itchiness

• Inflammation

• Anxiety

• Incorrect sensor glucose reading results in incorrect diabetes management

• Subject over-treating secondary to alarms which can result in

	Prevention and mitigation include: 

• Follow the provided user guides for insertions and care of sensors.

• If a sensor site becomes infected or inflamed, the sensor should be removed and another placed in a new location

• Base diabetes management on fingerstick readings and not sensor glucose values.

 
hyperglycemia or hypoglycemia
 
Anxiety associated with insertion
 
	
Risks with Transmitter	Prevention and Mitigation
Risks with Transmitter may include: 
 
Skin irritation or reaction to adhesives
 
Bruising
 
Discomfort
 
Redness
 
Pain
 
Rash
 
Infection
 
Irritation from tapes used with glucose-sensing products
 
Raised bump
 
Allergic reaction
 
Soreness or tenderness
 
Residual redness associated with adhesive and/ or tapes
 
Scarring
 
Scab
 
Blister
 
Itchiness
 
Inflammation
 
	Prevention and mitigation include: 
 
Follow the provided user guides.
 
Training on proper use of the transmitters.
 

Risks with Serter	Prevention and Mitigation
Risks with Serters may include: 
 
Improper insertion may lead to device performance issue or hyperglycemia
 
	Prevention and mitigation include: 
 
Follow the provided user guides for insertions and care of device.
 
Training on proper use of the Serter and skin preparation prior to insertion.
 

Risks with Finger Sticks	Prevention and Mitigation
Risks with frequent finger stick testing may include: 
 
Potential risks associated with frequent meter testing of blood glucose and blood ketones include discomfort and ecchymosis at tips of fingers
 
Potential risks associated with finger stick testing include discomfort and bruising
 
	Prevention and mitigation include: 
 
Follow the provided user guides for use of the study meter with fingerstick testing.
 
Training on proper use of the meter and fingerstick testing.
 

Risk with Closed Loop Therapy	Prevention and Mitigation
Risks with Closed Loop may include:	Prevention and mitigation include:


 
• Hypoglycemia
 
• Severe hypoglycemia
 
• Hyperglycemia
 
• Diabetic ketoacidosis User Entry Error             
 
◦ Patient administering boluses by entering false carb doses leading to hypoglycemia or hyperglycemia
 
◦ Patient entering false glucose values for any reason leading to hypoglycemia and hyperglycemia
 
◦ Patient entering false BG values for calibration leading to hypoglycemia or hyperglycemia
 
 
 
• Sensor failure resulting from patient failure to calibrate leading to hypoglycemia or hyperglycemia
 
• Sensor over-reading resulting in hypoglycemia
 
• Sensor under-reading resulting in hyperglycemia
 
• Sensor missed transmission, or any other fault resulting in no SG value, leading to hyperglycemia or hypoglycemia
 
• Voluntary insulin delivery (with the pump or with a syringe) immediately prior to entering Auto Mode may result in severe hypoglycemia despite shutting down insulin delivery by the algorithm
 
• Hypoglycemia related to patient taking insulin via injection while in Closed Loop (Auto Mode)
 
• Hypoglycemia or hyperglycemia related to entering or exiting Closed Loop (Auto Mode)
 
• Insulin over-delivery due to potential interference from acetaminophen
 
• Cyber security hacking into pump
 
	
 
• Follow the provided user guides for insulin pump management.
 
• Training prior to study on device use and diabetes management principles and told to call with problems.
 
• Check SMBG 4-6 times a day.
 
• Instructed to have glucose on hand for hypoglycemia
 
• Subjects will be instructed to consider avoiding the use of products containing acetaminophen
 
• If acetaminophen is taken, subjects will be instructed to use additional BG meter readings (they are not to calibrate with those readings) to verify their glucose levels.
 
• If acetaminophen is taken, subjects should consider exiting Auto Mode
 
• Pump has cybersecurity encryptions to prevent hacking.
 


Risks with hyperglycemia may include
 
 
• Diabetic ketoacidosis
 
• Symptomatic ketosis
 
• Cardiovascular event
 
	
Prevention and mitigation include:
 
 
• Follow the provided user guides for insulin pump management.
 

• Dehydration

• Potassium and sodium imbalance

• Shock

• Altered mental status

• Coma Acidosis

	

• Training prior to study device use and diabetes management principles.

• Check SMBG 4-6 times a day.

Risks with hypoglycemia may include: 

• Seizure

• Coma

• Altered mental status

• Loss of consciousness

• Cardiovascular event

• Death

• Risk of rebound hyperglycemia with ketosis

	Prevention and mitigation include: 

• Follow the provided user guides for insulin pump management.

• Training prior to study device use and diabetes management principles.

• Check SMBG 4-6 times a day.

• Instructed to have glucose on hand for hypoglycemia

Risk with Acetaminophen Use	Prevention and Mitigation
Potential risks with acetaminophen may include: 

• False elevation of sensor glucose readings. The level of inaccuracy depends on the amount of acetaminophen active in subject's body and may be different for each subject

	Prevention and mitigation include: 

• Follow the user guide

• Subjects should be instructed to consider avoiding the use of products containing acetaminophen

• If acetaminophen is taken, subjects should use additional BG meter readings (they are not to calibrate with those readings) to verify their glucose levels

• Subjects should consider exiting Auto Mode

Risks related to blood glucose meter use	Prevention and Mitigation
Risks with blood glucose meter use 

• Inaccurate blood glucose or no results

	Prevention and mitigation include: 

• Follow the provided user guides for use of the study meter

• Training on proper use of the meter

